Patients were selected among those who had applied to emergency service and evaluated by a pulmonary medicine resident or specialist. The general population of the study was made from the patients whose hospital admission to the COVID-19 ward was required after pulmonary medicine evaluation requested by an emergency medicine specialist. Inclusion criteria were being over 18 years old, approval given both written and orally for participation, COVID-19 positivity proven by reverse transcription-polymerase chain reaction (RT-PCR) testing, and deemed suitable for pulmonary function testing by a pulmonary medicine specialist. Exclusion criteria were planned mostly for optimal function testing, which included any pathological findings that impede pulmonary function testing such as chest deformity, an additional persistent pulmonary pathology that would prevent hospital discharge even after COVID-19 treatment, known severe pulmonary function loss (characterized by a FEV1 of %30 or less or being unable to participate in respiratory function testing), persistent COVID-19 findings which may affect respiratory functions (characterized by being bedridden or extended stay requirement due to desaturation not responding to nasal oxygen therapy) and former COVID-19 history.

Due to ethical considerations and the assumption that respiratory physiotherapy performed by the respiratory exerciser would be beneficial, all patients accepted into the study were offered enlistment to the treatment group. Those willing to participate in the study but refused device usage were accepted as the control group. Patients in the treatment group were asked to use the respiratory exerciser at least four times per day, with each session not lasting longer than 10 minutes and with at least an hour in between sessions.

Regardless of suitability for the study, all patients undergo a respiratory function test evaluation at the end of the first month, as per routine hospital approach to COVID-19 patients requiring hospital admission. The follow-up results of those who had participated were recorded from this evaluation. Additional follow-up was performed as a part of routine COVID-19 follow-up, such as an RFT at three months; however, these results were not a part of this study and thus were not accessed or recorded.

PEF, as both percentile and absolute value change, was accepted as the study's primary outcome. Mortality was considered as the secondary outcome parameter. The presence of known respiratory diseases was accepted as the main confounding parameter, and thus, as defined earlier, patients with known respiratory limitations had to be removed from the study. Other comorbidities were evaluated by Charlson Comorbidity Index (CCI). Forced Expiratory Volume (FEV) and Forced Vital Capacity (FVC) percentages were used to confirm the respiratory stability before COVID-19 diagnosis, values of both being over 80% was deemed normal. Demographic data was also included due to being required to calculate respiratory function thresholds.

Patients' data were retrieved from the hospital record system and from the respiratory function testing center. Demographic data, treatment modalities, and evaluation dates were also evaluated from electrical patient files from the hospital record system. Initial PEF results were taken from the patients' personal peak flow meter devices, and the final results were recorded from both hospital spirometer results and personal devices. Retesting was performed when a difference above 10% was observed between two different methods. If a difference was to be observed again, the result from the patient's device was accepted as the end result.

Selection bias was the main expected bias, and it was expected to be lessened by offering participation to all patients admitted to the COVID-19 ward. However, due to the study design, patients whose status was considered stable for outpatient treatment were excluded, which was expected to affect the results in favor of the treatment group. Additional treatment requirements were also considered another source of bias, as patients admitted to the COVID-19 ward often received more intensive treatment than outpatient regimens. However, the treatment regimen given to those admitted to the ward, which the study population consisted of, was assumed to be the same. Similarly, a combination of comorbidities was also considered another bias that might hinder a patient's ability to participate in respiratory testing, regardless of former capacity; thus, Charlson Comorbidity Index (CCI) was used to investigate comorbidities and ensure that comorbidities are present that patients remain within an acceptable range.

A total of 50 patients were assumed to be recruited into the study, with an even distribution between control and treatment groups. Excluding respiratory function test results, no further quantitative variable grouping was performed.

Descriptive analyses were utilized for data presentation. Nonparametric testing was utilized due to non-standard distribution and reduced sample size. Mann-Whitney U test was used to evaluate the distribution patterns between groups. Spearman's rho was utilized for correlation analysis. No subgroup analyses were planned for the study. If a patient had a missing PEF value for any reason, the patient would be removed from the study regardless of other values. As the second value of PEF would be recorded at the follow-up, any loss to follow-up would also be a reason for exclusion. IBM SPSS Statistics 25th Edition was used as the statistical program.

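### PEF change is the primary outcome in two unranked forms, one of them undefined, so either form could carry the claim and a split result has no planned conclusion

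*Combined protocol and SAP*

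**What the plan says.** The outcomes paragraph of the Methods says "PEF, as both percentile and absolute value change, was accepted as the" primary outcome. Neither form is ranked first, and 'percentile' is not defined.

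The same paragraph holds the only hints to its meaning. For FEV and FVC, "percentages were used to confirm the respiratory stability before COVID-19 diagnosis, values of both being over 80% was deemed normal". It adds: "Demographic data was also included due to being required to calculate respiratory function thresholds". Both point towards percent of predicted, but neither is linked to PEF and no reference equation is named.

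The Introduction describes comparing PEF at diagnosis with PEF after treatment. Its hypothesis speaks of better PEF results at one month, which is a direction and a level rather than a change.

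The statistical paragraph at the end of the Methods says "Nonparametric testing was utilized due to non-standard distribution and reduced sample size" and "Mann-Whitney U test was used to evaluate the distribution patterns between groups". It gives no significance level, sidedness, multiplicity rule or success rule. On size: "A total of 50 patients were assumed to be recruited into the study, with an even distribution between control and treatment groups".

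The Methods contain one rule for disagreeing results. It concerns the follow-up reading, where initial values came from "personal peak flow meter devices, and the final results were recorded from both hospital spirometer results and personal devices". It settles which instrument counts, not which form of the outcome counts.

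**The concern.** Two primary forms without a ranking leave three decisions open: which form decides, whether one success is enough, and what the percentage form is. Each can be settled after the results are known. If one form reaches significance and the other does not, the plan supports a positive claim and a negative one equally well.

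At stake are a somewhat raised false-positive rate, selective emphasis on the more favourable form, and a chance of a positive result that depends on an undefined word. In a study with a directional hypothesis, a named primary outcome and a between-group test, the reader needs to know in advance which comparison answers the question.

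**Working it through.** **The plan's own figure.** The total of 50 gives 50/2 = 25 per group. It cannot be reproduced, because no significance level, power, effect or SD is stated. At an assumed two-sided 0.05 and 80% power, 25 per group detects (1.960 + 0.842) × √(2/25) = 0.79 SD. This only shows what the size could deliver; it is not the plan's rationale.

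**The three candidate forms.** Let B and F be PEF at diagnosis and follow-up, and P the predicted PEF.
- Absolute change: F − B
- Change in percent of predicted: 100 × (F − B)/P
- Percent change from baseline: 100 × (F − B)/B

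Example, with P = 480 L/min and a rise of 15 points of predicted (72 L/min) in each patient:
- Baseline 65% of predicted: B = 312, so percent of baseline = 72/312 = 23.1%.
- Baseline 47% (one assumed SD of 18 lower): B = 225.6, so percent of baseline = 72/225.6 = 31.9%.

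The first two forms treat these patients alike and the third does not. So the meaning of 'percentile' matters.

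**Inputs to the simulation.** 25 v 25 is from the statistical paragraph. All else is assumed: two-sided 0.05 per test; P normal with mean 480 and SD 80 L/min; baseline 65% and follow-up 80% of predicted, SD 18; baseline/follow-up correlation r = 0.5 or 0.7; an effect of 0 or 12 points of predicted. There were 20,000 trials per setting, each form tested by Mann-Whitney U. Paired figures below are for r = 0.5 / 0.7.

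**No effect.** Simple bounds for 'either form wins' are 0.05 + 0.05 = 0.10 (Bonferroni) and 1 − 0.95² = 0.0975 (independent tests). The forms share the same readings, so the simulated figures are lower.

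| Pair | Correlation of forms | Either wins | Both must win |
|---|---|---|---|
| Absolute + percent of predicted | 0.98 / 0.97 | 0.057 / 0.060 | 0.040 / 0.036 |
| Absolute + percent of baseline | 0.85 / 0.83 | 0.063 / 0.065 | 0.035 / 0.031 |

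With skewed follow-up values, 35 v 15 allocation or SD 12, 'either' ranges over 0.054-0.069 and 'both' over 0.031-0.041.

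**12-point effect: power of each form.**
- Percent of predicted: 0.617 / 0.830
- Absolute: 0.589 / 0.801
- Percent of baseline: 0.457 / 0.649

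Percent of baseline against percent of predicted: 0.617 − 0.457 = 0.160 and 0.830 − 0.649 = 0.181. Across repeat runs the loss is about 15-18 points. It is 13-18 points in checks where the effect is instead fixed in L/min or proportional to baseline or follow-up, or with SD 12 and an 8-point effect.

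The spread within each form (for example 0.617 to 0.830) comes from the assumed r, not from the choice of form.

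**12-point effect: split results** (split = either − both).
- Absolute + percent of predicted: 0.644 − 0.563 = 0.081; 0.850 − 0.781 = 0.069 (0.070 before rounding).
- Absolute + percent of baseline: 0.606 − 0.440 = 0.166; 0.815 − 0.635 = 0.180.

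**Sensitivity to the spread of predicted PEF.** The first split depends on the assumed SD of P. With SD from 40 to 120 L/min it runs from about 4% to 12%, and absolute change has about 1-6 points less power than percent of predicted. The second split stays at about 16-19%.

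**The case against.** The strongest case against giving this much weight has four parts.

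**The better-supported reading makes the problem small.** If 'percentile' means percent of predicted, the forms correlate at 0.97-0.98, error under 'either' is 5.7-6.0% in the main setting, and their power differs by only a few points. This stands. The larger figures require percent of baseline, which the text does not favour.

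**The study is observational.** The control group was not randomised: "Those willing to participate in the study but refused device usage were accepted as the control group". A small error inflation is minor beside self-selection. This stands as to weight, but it does not supply a deciding form.

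**Nothing in the plan makes percent of predicted the right choice.** This also stands. Any single form, fixed in time, cures the defect.

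**Reporting both forms is good practice.** Agreed, and the fix keeps both. What is missing is which one decides.

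Two stronger readings are tempting. A reader might infer a false-positive rate near 10%. That needs nearly independent tests, and these two forms come from the same PEF readings. A reader might also infer from the past tense that the form was chosen after the data were seen. The documents do not say when PEF was compared by group.

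**Conclusion.** The gap in the text is certain: two primary forms, no deciding form, no definition of 'percentile', no significance level, and a test tied to neither form. Following the plan as written lets either form carry the claim and leaves a split without a conclusion.

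The size is modest and rests on the assumptions above; only 25 v 25 is the plan's own. Error is about 5.4-6.9% if either form may win. With a real effect, a split occurs in about 4-12% of trials under percent of predicted. It occurs in about 16-19% under percent of baseline, with the 15-18 point power loss that this form carries. The last two figures should not be quoted as the general size of the problem.

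A reader might infer that naming one form also deals with baseline differences between the groups. It does not. With no effect, a device group assumed 0.5 SD lower at baseline and the gap regressing as it does within groups, the percent-of-predicted change test has a false-positive rate of 0.136 / 0.098. That is confounding, a separate issue.

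Nor may disagreement between a baseline-adjusted analysis and the change-score test be read as proof of dependence on a baseline gap. With no true gap and a 12-point effect, ANCOVA and Mann-Whitney have power 0.75 / 0.89 and 0.61 / 0.82. They disagree in about 20% / 10% of trials, and still in about 15% / 7% when the observed gap is under 0.1 SD.

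**What to change.** - **Methods, outcomes paragraph.** Name one form as the single primary outcome before PEF is compared by group. A reasonable choice is change in PEF percent of predicted (follow-up minus diagnosis, with one stated reference equation for both readings), if the demographics it needs are recorded. Otherwise use absolute change in L/min. Define 'percentile'. Report the other form as supportive, with its estimate and 95% CI.
- **Methods, statistical paragraph.** Tie the Mann-Whitney U test to the primary form at two-sided 0.05. Report baseline PEF by group. A baseline-adjusted analysis is optional and a sensitivity analysis only, with no rule that disagreement indicates a baseline gap.
- **Introduction.** Word the hypothesis as change in PEF, to match the outcome.
- **If PEF has already been compared by group.** Report both forms and disclose that no deciding form was preset. Naming one at that stage would not control error.

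**Cost.** A few sentences; no new visit or PEF reading, and the planned test stays. One form loses primary status. Percent of predicted needs demographics including height, which the documents do not name. Falling back to absolute change costs about 1-6 points of power under the assumptions used here.

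### Patients choose their own group, but the plan specifies no measure of COVID-19 severity at admission, so confounding by severity could at best be partly reduced with the items it names

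*Combined protocol and SAP*

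**What the plan says.** All places below are in the Methods of the combined protocol and SAP.

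- **Group formation.** There is no randomisation: "all patients accepted into the study were offered enlistment to the treatment group", and "Those willing to participate in the study but refused device usage were accepted as the control group".
- **Confounders.** "The presence of known respiratory diseases was accepted as the main confounding parameter", and it is handled by exclusion. Other comorbidity is summarised by the Charlson index. FEV and FVC "percentages were used to confirm the respiratory stability before COVID-19 diagnosis". Demographics are kept because they are needed to calculate lung-function thresholds.
- **Data sources.** "Demographic data, treatment modalities, and evaluation dates were also evaluated from electrical patient files from the hospital record system". For the primary outcome, "Initial PEF results were taken from the patients' personal peak flow meter devices"; the final value comes from the spirometer and the personal device.
- **Eligibility.** Patients with persistent COVID-19 findings are excluded, defined as being bedridden or having an "extended stay requirement due to desaturation not responding to nasal oxygen therapy".
- **Bias paragraph.** It discusses ward versus outpatient status and treatment intensity, and assumes that everyone on the ward received the same regimen. It does not discuss differences in severity between those who accept the device and those who refuse it.
- **Analysis.** A Mann-Whitney U test between groups and Spearman's rho, with no covariate model. The total of 50 patients is assumed to split evenly.

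**The concern.** When patients choose their own group, the main protection against confounding is to measure what drives both the choice and the outcome, and then to adjust for it. How ill a patient is at admission is an obvious candidate. It may affect willingness to take on at least four exercise sessions a day, and also how far PEF has fallen and how much of it returns by one month. The plan itself treats severity as relevant, since it excludes some patients because their persistent findings may affect respiratory function.

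That exclusion narrows the range of severity but does not balance it between self-chosen groups. Offering participation to all ward patients concerns entry to the study, not who accepts the device afterwards. If acceptors and refusers differ in severity, their expected PEF change differs with no device effect at all. Without a severity measure, no one could later tell in which direction.

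This is partly separate from the choice of test. Replacing the Mann-Whitney test with a model would not help with severity unless a severity variable is available to put in it.

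**Working it through.** **Named covariates against the state at admission**

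| Item in the Methods | What it describes |
|---|---|
| Known respiratory disease | Before the illness; handled by exclusion |
| Charlson index | Chronic comorbidity |
| FEV and FVC percentages | Lung function before COVID-19 |
| Demographics | Fixed characteristics |
| Treatment modalities | Possibly related to severity; undefined, no time point, regimen assumed the same |
| Initial PEF | Measured during the illness; effort-dependent; enters the planned outcome only through the change |

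No row is a specified measure of acute severity. The last two are possible proxies.

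**Scale.** The plan gives no alpha, power, effect size or SD, so the total of 50 cannot be reproduced. Assuming two-sided alpha 0.05 and 25 per group, the difference detectable with 80% power is (1.960 + 0.842) × √(2/25) = 2.802 × 0.283 = 0.79 SD.

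**Unadjusted bias.** The inputs are assumptions and none is in the documents: half the patients are more severe, severity shifts PEF change by 0.4 to 0.8 SD, and 65% of the more severe and 35% of the less severe accept.

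1. Share more severe among acceptors: 0.5 × 0.65 / (0.5 × 0.65 + 0.5 × 0.35) = 0.65. Among refusers it is 0.35.
2. Spurious difference = (0.65 − 0.35) × severity effect = 0.30 × 0.4 to 0.30 × 0.8 = 0.12 to 0.24 SD.
3. Standard error = √(2/25) = 0.283 SD.
4. Two-sided rejection with no device effect (normal approximation) = 1 − Φ(1.96 − bias/0.283) + Φ(−1.96 − bias/0.283). This gives 7.1% at 0.12 SD and 13.6% at 0.24 SD.
5. With 70% versus 30% acceptance: 0.40 × 0.4 to 0.40 × 0.8 = 0.16 to 0.32 SD, and 8.7% to 20.5%.

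If the SD is read as the SD within a severity stratum, the upper values fall to 12.5% and 18.6%. The sign reverses if the less severe accept more often.

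**What is left after adjusting for proxies.** Take two conditionally independent proxies, standing for initial PEF and treatment modalities, each with an assumed correlation r with severity. The share of bias remaining is 1 / (1 + 2r²/(1 − r²)).

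| r | Share remaining |
|---|---|
| 0.3 | 1 / (1 + 0.18/0.91) = 84% |
| 0.5 | 1 / (1 + 0.50/0.75) = 60% |
| 0.7 | 1 / (1 + 0.98/0.51) = 34% |

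The formula is for continuous severity, so applying it to the two-level case above is approximate:

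- 0.12 to 0.24 SD becomes 0.34 × 0.12 = 0.04 to 0.84 × 0.24 = 0.20 SD. With the same standard error, false positives are about 5% to 11%.
- 0.16 to 0.32 SD becomes 0.05 to 0.27 SD, and false positives are about 5% to 16%.

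**Simulation check** (25 per group, no device effect, 1,500 runs per setting, assumed inputs). With a 0.8 SD severity imbalance and a 0.5 correlation between severity and outcome, the unadjusted bias was about 0.40 SD and the Mann-Whitney test rejected in about 26% of runs. Adjusting for both proxies at r = 0.3, 0.5 and 0.7 left 0.33, 0.24 and 0.15 SD, with rejection in about 20%, 12.5% and 8%. With a 0.5 SD imbalance and a 0.3 correlation, the unadjusted bias was about 0.15 SD and the Mann-Whitney rejection rate about 7% to 8%.

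**The case against.** Four points on the other side have force.

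- **The data list is not clearly closed.** It omits the Charlson index, FEV, FVC and mortality, all of which the plan uses. A reader might infer that severity was never extracted. The text supports only that no such measure is specified.
- **Treatment modalities may include oxygen.** The term is undefined, so it is not established that oxygen need goes unrecorded. Even so, the field has no stated time point, and the plan assumes a uniform ward regimen, so it does not use the field to measure severity.
- **Initial PEF carries part of the pathway.** If sicker patients start lower and have more to regain, adjusting for baseline PEF addresses that part. What remains is any effect of severity that a single effort-dependent reading does not capture. The plan contains no such adjustment.
- **The range of severity on the ward is not given.** A reader might infer from the exclusion that admitted patients run from no oxygen to nasal oxygen only. The criterion concerns persistent findings and sets no ceiling on support at admission.

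It can also be said that the unadjusted comparison is the operative flaw. That is true of the plan as written, but correcting the test alone would leave no specified severity variable to adjust for.

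**Conclusion.** The point holds in a limited form. Groups are self-selected, no measure of severity at admission is specified, and the planned test adjusts for nothing. Followed as written, the plan leaves confounding by severity in the primary comparison.

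A reader might go further and conclude that the named data are useless against this bias. The documents do not support that, because initial PEF and treatment modalities could remove some of it. The supportable statement is that they cannot be relied on to remove all of it.

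Neither size nor direction is known. The 0.12 to 0.24 SD and 7% to 14% are unadjusted figures that rest wholly on the assumed acceptance gap and severity effect; they do not measure what would remain after adjustment. A bias of that size is 15% to 30% of the 0.79 SD detectable at 25 per group (0.12/0.79 and 0.24/0.79). This is a worthwhile and cheap improvement. It does not show that a result from this study would be wrong.

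**What to change.** 1. Extract two items from the hospital record system, both dated before the device is offered: oxygen requirement at admission, in categories that cover all levels of support (none / nasal / more than nasal), and the first recorded saturation, noting whether it was taken on room air.
2. Define what treatment modalities contains and the time it refers to.
3. Tabulate both severity items by group.
4. Add an adjusted comparison of PEF change with admission oxygen requirement and baseline PEF as covariates.
5. State that confounding by motivation or other reasons for refusal remains after this adjustment.

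The cost is two extra fields from records already accessed and, for oxygen requirement, one or two degrees of freedom with 50 patients (two if all three categories are kept). There is no new procedure or patient contact. Some precision is lost if severity turns out to be balanced. The documents do not say that admission oxygen data are complete in the records, so check this first.

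### Co-treatment is assumed equal between device users and refusers although treatment data are extracted, leaving a potential confounder of the PEF comparison unchecked

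*Combined protocol and SAP*

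**What the plan says.** All of the relevant text is in the Methods section of the combined protocol and SAP.

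- **Group formation.** Every participant was offered the device. "Those willing to participate in the study but refused device usage were accepted as the control group".
- **Data sources.** "Demographic data, treatment modalities, and evaluation dates were also evaluated from electrical patient files from the hospital record system". The level of detail is not stated.
- **Bias paragraph.** "Additional treatment requirements were also considered another source of bias". The reason given is that ward patients tend to be treated more intensively than outpatients. The paragraph then closes the issue: "the treatment regimen given to those admitted to the ward, which the study population consisted of, was assumed to be the same". Comorbidity, named as a bias in the same paragraph, is measured with the Charlson index.
- **Statistical paragraph.** "Mann-Whitney U test was used to evaluate the distribution patterns between groups". Otherwise it names only descriptive analyses and Spearman correlation, and it plans no subgroup analyses. It names no comparison of treatments between groups, and no adjustment, stratification or matching.
- **Sample size.** "A total of 50 patients were assumed to be recruited into the study, with an even distribution between control and treatment groups". No alpha, power, effect size or SD is given.

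**The concern.** The plan recognises a source of bias and answers it with an assumption that its own data could test. The argument given concerns ward patients against outpatients. The comparison actually made is device users against refusers, all of them on the ward. Restriction removes the first contrast and says nothing about the second.

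People who accept an offered treatment aid may differ from those who decline it in severity and in the other treatment they receive. If one group had more intensive COVID-19 treatment and that treatment affects recovery of peak flow, part of its effect would be credited to the device, or would hide a device effect. A Mann-Whitney test takes no covariates and cannot separate the two. What is at stake is whether a difference in PEF change can be read as an effect of the device.

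**Working it through.** The documents state no figure for this point, and N = 50 cannot be reproduced because none of its inputs are given. The check is therefore a reading of the text, followed by an illustration in which only the 25 per group comes from the plan.

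**1. Does the restriction answer the bias?** The ward requirement holds setting constant. The exclusion of patients whose desaturation does not respond to nasal oxygen narrows severity, but patients whose desaturation does respond remain eligible. Treatment can therefore still vary within the ward, and nothing in the design ties it to be equal across the two self-selected groups.

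**2. Size of the possible bias.** For a binary co-treatment used by a share p1 of users and p0 of refusers, with effect g on PEF change in SD units:

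bias = (p1 − p0) × g

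Assumed ranges: imbalance 0.10 to 0.30, effect 0.3 to 0.8 SD.

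- Low end: 0.10 × 0.3 = 0.03 SD
- Middle: 0.20 × 0.5 = 0.10 SD
- High end: 0.30 × 0.8 = 0.24 SD

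**3. Yardstick.** The detectable difference with 25 per group, assuming two-sided alpha 0.05 and 80% power, is (1.960 + 0.842) × √(2/25) = 0.79 SD for a t test. Dividing by √0.955, the Mann-Whitney efficiency under normality, gives 0.81 SD. The biases above are then 0.03/0.81 = 4%, 0.10/0.81 = 12% and 0.24/0.81 = 30% of it.

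**4. Effect on the test.** This is a simulation of the Mann-Whitney test with 25 per group, a normal outcome with SD 1, no device effect and 20,000 runs per scenario. It gives the share of runs rejected at 0.05:

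| Use, users vs refusers | g = 0.3 | g = 0.5 | g = 0.8 |
|---|---|---|---|
| 50% vs 50% | 4.7% | 4.9% | 4.6% |
| 60% vs 40% | 5.1% | 5.9% | 7.6% |
| 70% vs 30% | 6.3% | 9.9% | 17.1% |
| 80% vs 20% | 8.8% | 16.6% | 34.1% |

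The last two rows are imbalances of 40 and 60 points, outside the range used in step 2. They show what a severe imbalance would do, not what is expected.

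**5. Can a significance test of imbalance settle it?** Not at this size. For 60% vs 40% use with 25 per group and two-sided alpha 0.05, the null standard error is √(2 × 0.5 × 0.5/25) = 0.141 and the alternative standard error is √(2 × 0.24/25) = 0.139. Then (0.20 − 1.960 × 0.141)/0.139 ≈ −0.56, which is power of about 29%. A non-significant p-value would give little reassurance.

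**The case against.** The strongest reply has four parts.

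- **The design already limits the problem.** Restriction to the ward and the severity exclusions are real controls that reduce the plausible imbalance. This stands as a reason to expect a modest bias. It does not make users and refusers alike.
- **The plan does not rule out a treatment table.** Treatment modalities are extracted and descriptive analyses are planned, so such a table might appear. That is fair, but none is named, and a table alone would not adjust the PEF comparison.
- **Adjustment may achieve little.** Recruitment follows emergency evaluation and the first PEF is taken at diagnosis, so much treatment may start after enrolment, when adjusting for it is not appropriate. The most used treatment may be near-universal, and choosing it on that basis would mean choosing from the data. The plan mentions evaluation dates but not treatment start dates. All of this stands and shapes the fix: the covariate has to be conditional, and the adjusted model supportive only.
- **Co-treatment is one instance of a wider problem.** The comparison of self-selected groups is unadjusted throughout, and severity and motivation are untouched by this fix. That is true. It limits what the fix delivers, but is no reason to leave a recorded factor unchecked.

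A reader might go further and infer that treatment did differ between the groups, or that the false-positive rate is inflated to the higher values in the simulation. The documents support neither. They report no treatment by group and no effect of any treatment on PEF, and the higher rejection rates come from assumed imbalances of 40 points or more.

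**Conclusion.** The point holds as a gap in the plan, not as a demonstrated bias. Equality of co-treatment between device users and refusers is assumed where the plan's own data extraction should allow it to be examined, and the between-group test cannot account for any difference. Over the assumed range the bias is 0.03 to 0.24 SD, which runs from negligible to about a third of what the study could detect, and it could favour either group. Those figures rest on assumed imbalance, treatment effect, alpha and power; the true size cannot be computed from the documents. The change is worth making because it costs little and bears on what may be concluded from the main comparison.

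**What to change.** 1. Replace the equality assumption in the Methods section with a prespecified table of recorded treatment modalities by group. Show differences in proportions and do not rely on p-values. Where the records give dates, split treatments into those started before and after enrolment.
2. Keep the Mann-Whitney test and add one supportive adjusted comparison of PEF change with baseline PEF as a covariate. Include a single treatment indicator only if that treatment was in place before enrolment and its use varies. Name it in advance on clinical grounds, not because it turns out to be the most used.
3. Describe treatment started after enrolment, without adjusting for it.
4. State that, if treatments differ by group, a PEF difference cannot be attributed to the device alone.

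**Cost.** One table and a small secondary model that uses one or two degrees of freedom in about 50 patients. The split by start date depends on the records holding those dates, which the plan does not confirm. Confounding by unmeasured severity and motivation would remain.
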